4.5. Dose Justification

This study is planned to test single doses of GSK3039294 and repeat doses up to the maximum tolerated dose or the maximum allowable dose based on pre-clinical findings. The intention is to target the PK exposure of CPHPC seen in previous clinical studies producing the SAP depletion required for future studies with anti-SAP mAb.

Part A

The starting dose in Part A is planned to be 200mg of GSK3039294. This dose is selected using the PK/PD model that was developed for CPHPC (active molecule) [Sahota, 2015], adjusted for the oral absorption of GSK3039294 and the conversion of GSK3039294 to CPHPC. PK in pre-clinical species (rat and dog) show a very fast and complete conversion of GSK3039294 into CPHPC. Several marketed pro-drugs (viread, cerebyx, spectracef, hepsera) have either a fast and complete conversion into the active compound, or a tmax of the active compound that is within a few hours consistent with fast conversion.

Assuming fast and complete oral absorption of GSK3039294 and fast and complete conversion of GSK3039294 into CPHPC, then both processes are described by a single first-order process (Ka) and high bioavailability (F). For the purposes of dose estimation Ka and F have been assumed to be high: 1.3/hr and 100%, as this will result in the highest exposures to CPHPC possible. Distribution and elimination of CPHPC is expected to be the same, regardless of IV administration of CPHPC or oral administration of the pro-drug (GSK3039294). Therefore, distribution and elimination parameters, as well as between subject variability, were set to the estimates from the analysis of CPHPC itself.

The NOAEL for GSK3039294 in preclinical species is set to 1000 mg/kg/day, which is associated with CPHPC exposure of AUC[0-24] of 250 µg.hr/mL and Cmax of 22.1 µg/mL. In the rat cardiovascular changes were observed at concentrations of about 6 µg/mL. These changes were not observed in studies with dogs, and are considered species specific, however, to confirm there are no cardiovascular changes in clinic, the SD dose escalation in Part A will start at a dose that is predicted to result in CPHPC concentrations that are lower than 6 µg/mL.

Using the PK/PD model the concentration-time profiles of CPHPC after a single dose of GSK3039294 were simulated, and Cmax and AUC[0-inf] were derived. For a dose of 200 mg, this resulted in a predicted AUC[0-inf] of 14.5 µg.hr/mL (95% CI of 9.5-22.4 µg.hr/mL) and a predicted Cmax of 3.4 µg/mL (95% CI of 2.1-5.0 µg.hr/mL).

The next doses in Part A will be determined based on the data of the preceding dosing sessions. All available PK data will be analysed (see Section 9.3.2.1), and the next dose will be such that the median Cmax will be about 6 µg/mL, and the predicted 95% CI will not exceed preclinical Cmax and AUC limits.

The highest dose in Part A will not exceed pre-clinical safety exposure limits of AUC[0-24] of 250 µg.hr/mL and Cmax of 22.1µg/mL.

Part B

The dose level for Cohort 3 in Part B will be determined based on the PK data obtained in Part A, by analysing all available PK data from Part A and subsequently predicting concentration-time profiles at steady state after repeat dosing. Table 5 shows examples of dose levels and frequencies with predicted AUC[0-24] and C_{max} at steady state, using the PK/PD model that was developed for CPHPC (active molecule) [Sahota, 2015], adjusted for oral absorption and conversion of GSK3039294 into CPHPC. The PK data from Part A will be used to obtain estimates for K_a and F.

Table 5 Example Doses And Predicted Exposures For Part B

Dose	K _a	F	AUC[0-24h] (µg.hr/mL) ^{*)}	C _{max} (µg/mL) ^{*)}
Cohort 3				
300mg OD	1.3	1	23.4 (15.3-35.9)	5.20 (3.32-7.84)
300mg OD	1.3	0.5	11.4 (7.36-18.1)	2.61 (1.72-3.86)
300mg OD	0.6	1	22.8 (14.7-36.2)	3.83 (2.73-5.42)
Cohort 4a (first part)				
300mg BID	1.3	1	45.7 (29.4-72.5)	5.49 (3.75-8.05)
300mg BID	1.3	0.5	22.8 (14.7-36.2)	2.74 (1.87-4.02)
300mg BID	0.6	1	45.7 (29.4-72.5)	4.09 (2.94-5.76)
Cohort 4a (last part)				
600mg BID	1.3	1	91.3 (58.9-145)	11.0 (7.50-16.1)
600mg BID	1.3	0.5	45.7 (29.4-72.5)	5.49 (3.75-8.05)
600mg BID	0.6	1	91.3 (58.9-145)	8.19 (5.88-11.5)

^{*)} Predicted AUC[0-24] and C_{max} at steady state; presented are mean and 95%CI

The dose levels for subsequent cohorts in Part B will be determined based on the PK data from Part A (single dose), and cohort 3 in Part B (multiple dose). All available PK data will be analysed (see Section 9.3.2.1). The dose levels and dosing frequencies will be chosen such that the predicted 95% CI of C_{max} and AUC at steady state will not exceed preclinical C_{max} and AUC limits (22.1 µg/mL and 250 µg.hr/mL, respectively).

Part C

GSK3039294 will be administered at the predicted optimal clinical dose for 21 days. This dose will be determined using the PK/PD model that was developed for CPHPC (active molecule) [Sahota, 2015]. Using all available PK and plasma SAP (PD) data from Parts A and B, the model will be adjusted for the oral absorption of GSK3039294 and the conversion of GSK3039294 to CPHPC. Plasma concentration-time profiles of CPHPC as well as the plasma SAP time course after repeat dosing with GSK3039294 will be predicted in order to determine the optimal clinical dose and dose frequency. The dose level and frequency will be chosen such that the predicted 95% CI of C_{max} and AUC at steady state will not exceed preclinical C_{max} and AUC limits (22.1 µg/mL and 250 µg.hr/mL, respectively). See Section 9.3.2.1 for further details of the analysis.

4.6. Benefit:Risk Assessment

GSK3039294 is an oral prodrug of CPHPC (GSK2315698). CPHPC has been associated with a good safety profile in clinical studies to date (see Investigator's Brochure)

There is no clinical benefit to either healthy volunteer subjects or systemic amyloidosis patients in achieving plasma SAP depletion during any Part of the study.

A NOAEL of 1000 mg/kg/day has been identified in Wistar rats based upon adverse findings as regards urine biochemistry in the absence of any identified pathological changes within the kidney using light microscopy techniques. Close monitoring of plasma and urine biochemical parameters, including renal function and proteinuria surveillance, will be performed in all Parts of the study including in systemic amyloidosis patients in Part C (see Section 7.1 & Section 7.5).

The release of CPHPC from GSK3039294 will be accompanied by the release of 2 molecules of formaldehyde. Formaldehyde is generated by endogenous human basal metabolism in substantial amounts, (approximately 50g per day). For a dose of 1.2 g per day (a dose not likely to be exceeded in this study), the total amount of formaldehyde generated would be around 120mg. In addition, a number of prodrug compounds such as Viread, Cerebyx, Spectracef and Hepsera releasing up to 120mg/day of formaldehyde have been described in the literature and there have been no specific human toxicology findings [Dhareshwar, 2008] associated with this upper level of formaldehyde release from their metabolism. Exogenous production of formaldehyde from either food stuffs or licensed prodrugs is not known, to date, to cause detectable organ or physiological dysfunction in humans.

Summaries of findings from non-clinical studies conducted with GSK3039294 can be found in the Investigator's Brochure. Summaries of findings from both clinical and non-clinical studies conducted with GSK2315698 can be found in the Investigator's Brochure. The following section outlines the risk assessment and mitigation strategy for this protocol:

4.6.1. Risk Assessment

Potential Risk of Clinical Significance	Summary of Data/Rationale for Risk	Mitigation Strategy
Investigational Product (IP) [e.g., GSK3039294, GSK2315698]		
Generation of formaldehyde upon transformation of GSK3039294 (prodrug) into active (GSK2315698).	Refer to Section 4.5	Maximum dose is likely to be below 1.2g, which releases similar amounts of formaldehyde as existing prodrugs releasing formaldehyde.
GSK2315698 - Epistaxis	
Small volume nose bleeds have been noted in a few patients which have been self-limited and not associated with any evidence of thrombocytopenia or coagulopathy.
 
The relationship to GSK2315698 is unclear but subjects are closely monitored for bleeding.
	
Observe for incidence / severity
 
Monitoring of haemoglobin & platelets

Potential food effect on PK of GSK3039294 (and subsequent GSK2315698)	Based on the physical-chemical properties of GSK3039294 it is not expected that the PK will be affected by food. However, as it is not feasible to give bid or tid dosing under fasted conditions, administration of GSK3039294 in Weeks 2 and 3 of Part B and in Part C will be without restrictions with respect to meal times.	A potential effect of food will be explored in this study (Cohort 3 of Part B). If the food effect exploration shows an effect of food on the PK of GSK3039294 (and subsequently GSK2315698), a formal food effect study will be considered.

Potential Risk of Clinical Significance	Summary of Data/Rationale for Risk	Mitigation Strategy

Preclinical finding of potential nephrotoxicity of GSK3039294
	
Following 4 weeks oral dosing in rats, minor changes in urine composition comprising of low pH in males given ≥ 300 mg/kg/day (mean pH was 5.8 and 6.4 at 1000 mg/kg/day or control respectively) and females given 1000 mg/kg/day (mean pH was 5.6 and 5.9 at 1000 mg/kg/day or control respectively), an increase in total protein excretion in both sexes given 1000 mg/kg/day (up to 1.48X control) and increased specific gravity, creatinine and glucose output for males given 1000 mg/kg/day (1.02X, 1.14X and 1.22X control, respectively). These changes were considered not biochemically concerning, and were not associated with any renal pathological findings on H&E staining of rat kidney paraffin sections.
 
Additionally, no change in any urinalysis parameters was observed in the dog 28 day toxicity study with GSK3039294 at doses ≤ 1000 mg/kg/day.
 
Overall, in the absence of any renal pathological changes under light microscopy, the significance of these rat renal biochemical changes is unclear.
	
Precautions as listed in Section 7.4 to detect signals of potential nephrotoxicity from GSK3039294 in humans at the earliest time point possible during both single and repeat dose administration in both healthy volunteer subjects and systemic amyloidosis patients.

Potential Risk of Clinical Significance	Summary of Data/Rationale for Risk	Mitigation Strategy

Preclinical finding of haematologic effects associated with GSK2315698
	
In toxicology studies using IV GSK2315698, minor reductions in red cell parameters were observed in female dogs given 200 mg/kg/day for 4 weeks. A 34% increase in platelet count was seen in rats receiving 400 mg/kg/day for 8 days.
 
Some trends (haemoglobin increased; white cells and platelets decreased) within the reference range were observed in a single dose study in healthy volunteers (CPH113776). The clinical significance of these observations is not clear and similar changes were not observed in the patient study (CPH114527).
 
Therefore, at this time, it is felt to be very unlikely that GSK2315698 (CPHPC) has any haematological toxicity properties in human subjects.
	
Haematological parameters will be monitored in the clinic.
 
Dosing not to exceed the existing NOAEL.


Preclinical finding of testicular changes associated with GSK2315698
	
In one study in male rats (but not in another similar study), testicular changes (seminiferous tubular degeneration/atrophy, reduced spermatozoa, shedding of spermatogenic cells) were observed at the highest dose tested (400 mg/kg/day for 28 days). No testicular changes were observed in a rat 26 week study (terminated at week
	
The highest dose of GSK3039294 will not yield exposures of GSK2315698 exceeding a predicted mean AUC₀₋₂₄ of 145 ug*h/mL and C_{max} of 6.05 ug/mL based on the NOAEL in the rat 28 day IV repeat dose studies, and therefore the potential risk to humans during the proposed short term dosing is considered very low

Potential Risk of Clinical Significance	Summary of Data/Rationale for Risk	Mitigation Strategy
	
21) at GSK2315698 doses \leq 1000 mg/kg/day.
 
No testicular changes were observed in rat 28 day study with GSK3039294 at doses \leq 1000 mg/kg/day. In the dog no testicular changes have been observed with GSK2315698 or GSK3039294 at doses of \leq 200 mg/kg/day and \leq 1000 mg/kg/day, respectively.
	

Preclinical finding of cardiovascular changes associated with GSK2315698.
	
Preclinical finding in preliminary cardiovascular screen (rat only) of blood pressure, pulse pressure, heart rate increase and QA interval reduction associated with GSK2315698 (See IB for further information).
 
No arrhythmogenic safety signals were detected
	
Cardiovascular parameters, including blood pressure and heart rate, will be closely monitored in the clinical study.

Cardiac arrhythmias identified on 24-hour Holter after single dose administration of GSK3039294 in Part A of this study.
	
Four (4) asymptomatic, hemodynamically stable arrhythmias in 3 healthy volunteer subjects were seen on 24-hour Holter monitoring after single dose administration of GSK3039294 in Part A. 3 / 4 events were atrial tachycardias, and 1 / 4 event was a single 3.4 second episode of a AIVR (5 beats). All SVT (atrial) events were less
	
Supraventricular or ventricular arrhythmia exclusion criterion. Continuous telemetry at in-patient dosing.
 
Sentinel subject (systemic amyloidosis patient with known cardiac amyloid) in Part C for cardiac evaluation and monitoring prior to further recruitment.

Potential Risk of Clinical Significance	Summary of Data/Rationale for Risk	Mitigation Strategy
	
than < 11 seconds in duration.
 
One healthy volunteer subject had two separate arrhythmic events which consisted of a single episode of atrial tachycardia 10 minutes after administration of GSK3039294 - when neither prodrug or CPHPC were detectable - followed by a single 5-beat episode of AIVR approximately 12 hours later.
	
Subjects will be withdrawn from the study if the Investigator deems any cardiac AE to be clinically concerning, and / or triggers the measurement of plasma hs-cTn to exclude the possibility of arrhythmia-associated myocardial ischemia / injury (see Section 5.4.4. & Section 7.3.7.).

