6.3. Planned Dose Adjustments

This protocol allows some alteration from the currently outlined dosing schedule, but the maximum daily dose will not exceed pre-clinical exposure limits (C_{max} of 22.1 µg/mL and AUC_[0-24] of 250 µg.hr/mL).

The decision to proceed to the next dose level of GSK3039294, will be made by the GSK Study Team and the investigator based on safety, tolerability and preliminary pharmacokinetic and/or pharmacodynamic data (Parts B and C) obtained in at least 6 subjects at the prior dose level (see Section 10.7.1). The actual doses to be administered may be adjusted based on safety, tolerability and preliminary pharmacokinetic and/or

pharmacodynamic data at previous dose levels; these dose adjustments may involve either an increase or a decrease in the planned dose.

The dosing schedule may also be adjusted to expand a dosing cohort to further evaluate safety, pharmacokinetic and/or pharmacodynamic findings at a given dose level, or to add cohorts to evaluate additional dose levels. The study procedures for these additional subject(s) or cohort(s) will be the same as that described for other study subjects.

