9.3.2.1. Pharmacokinetics and pharmacodynamics

To inform dosing decisions for subsequent dosing sessions in Part A, individual values of C_{max} and AUC_[0-inf] will be derived by means of non-compartmental analysis. Assuming linear kinetics, the next dose will be such that the 95%CI of C_{max} and AUC will not exceed preclinical safety limits (22.1 µg /mL and 250 µg.hr/mL, respectively).

To inform dosing decisions for subsequent study parts, GSK2315698 concentration data and plasma SAP levels will be analysed using the PK/PD model that was developed for GSK2315698 [Sahota, 2015]. Based on pre-clinical data it is expected that the conversion of GSK3039294 to GSK2315698 is very fast. Therefore, it can be assumed that this conversion will occur mainly during the absorption phase, and that the

distribution and elimination of GSK2315968 are not altered. Therefore, all distribution and elimination parameters (PK/PD) will be fixed to the reported parameter estimates, and only bioavailability (F) and absorption related parameters (e.g. Ka) will be estimated. Nominal time points will be used for this interim analysis. This updated model will be used to simulate concentration-time data and plasma SAP levels using different dose levels and dosing regimens, which will be used to inform dosing decisions for subsequent dosing sessions, cohorts and study parts.

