10.7.1. Dose Escalation Committee

The decision to proceed to the next dose level of GSK3039294 in Parts A and B, or to proceed to the next study part will be made by a Dose Escalation Committee (DEC) consisting of the Principal Investigator, Medical Monitor, GSK Study Team Leader, GSK Pharmacokineticist and GSK Statistician (or appropriate designee's).

For Part A, dose escalation decisions will be based on data obtained from 6 or more subjects receiving GSK3039294 at the prior dose level(s). The review data set will at a minimum consist of all available PK data, adverse events, flagged vital signs, flagged findings during continuous cardiac monitoring (telemetry), ECG and laboratory findings.

The decision and selection of dose to proceed to Part B as well as any dose escalation decisions, will be made by the DEC based on all available PK data, the listings of any adverse events, flagged vital signs, flagged findings during continuous cardiac monitoring (telemetry), ECG and laboratory findings.

The decision and selection of dose to proceed to Part C, will be made by the DEC based at a minimum on available PK data, the listings of any adverse events, flagged vital signs, flagged findings during continuous cardiac monitoring (telemetry), ECG and laboratory findings, together with any available PD data from the dose levels investigated in Part A, and available PK, the listings of any adverse events, flagged vital signs, flagged findings during continuous cardiac monitoring (telemetry), ECG and laboratory findings, together with any available PD data from the dose levels investigated in Part B.

For further details related to the planned PK and PK/PD analyses to support the dose escalations, see Section 9.3.2.1. A maximum C_{max} of 22.1 µg/mL and AUC_[0-24] of 250 µg·hr/mL will not be exceeded in any cohort or study part.

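### The exposure cap behind the "very low" testicular risk in Section 4.6.1 (mean Cmax 6.05, AUC 145) is absent from the dose-setting rules, which stop only at 22.1 and 250

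*Protocol*

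**What the plan says.** **The commitment.** In the row on testicular changes, Section 4.6.1 gives one mitigation. The highest dose is not to produce predicted mean CPHPC exposure above an AUC0-24 of "145 ug*h/mL and C_{max} of 6.05 ug/mL based on the NOAEL in the rat 28 day IV repeat dose studies". The risk is called very low as a consequence of that limit.

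**The dose-setting rules.** These use a different pair of numbers, which Section 4.5 derives from the GSK3039294 NOAEL of 1000 mg/kg/day: Cmax 22.1 µg/mL and AUC0-24 250 µg·h/mL.

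- Section 4.5, Part C: "The dose level and frequency will be chosen such that the predicted 95% CI of C_{max} and AUC at steady state will not exceed preclinical" limits of 22.1 and 250. Part B has the same rule.
- Section 6.3: the "maximum daily dose will not exceed pre-clinical exposure limits (C_{max} of 22.1" µg/mL, with an AUC counterpart of 250).
- Section 10.7.1: the 22.1 and 250 maxima "will not be exceeded in any cohort or study part".
- Section 9.3.2.1, for dosing sessions within Part A only: "the next dose will be such that the 95%CI of C_{max} and AUC will not exceed preclinical safety limits (22.1" µg/mL, and 250 for AUC). Its text on later study parts names no numerical limit.

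Section 4.5 also sets an aim for Part A: "the next dose will be such that the median Cmax will be about 6" µg/mL. The Part B and Part C text has no equivalent.

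**The concern.** The Cmax limits differ by a factor of 3.65 (22.1/6.05) and the AUC limits by 1.72 (250/145). The stricter pair appears only in the risk table. Section 10.7.1, which tells the Dose Escalation Committee what must not be exceeded, gives the looser pair and refers onward to Section 9.3.2.1, which does not contain the stricter one either.

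A committee applying its own rules correctly could therefore approve a repeat dose that invalidates the stated basis for the risk conclusion. The row's mitigation is an exposure limit alone: the safety laboratory panel in Table 7 contains no male reproductive test. The doses still to be chosen are the 7-day and 21-day regimens, to which a 28-day rat finding is most relevant, and Section 4.6.2 expects no medical benefit for participants.

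**Working it through.** **Inputs.** The cap on the predicted mean comes from Section 4.6.1 (Cmax 6.05, AUC 145). The rule on the upper 95% limit comes from Section 4.5 (Cmax 22.1, AUC 250). Predicted steady-state means with 95% intervals come from Table 5. Both Section 4.6.1 and Table 5 refer to predicted means, so the comparison is like for like.

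**Reproducing Table 5.** Section 9.3.2.1 assumes linear kinetics. Doubling the 300 mg BID rows gives Cmax 2 × 5.49 = 10.98 (stated 11.0) and 2 × 4.09 = 8.18 (stated 8.19), and AUC 2 × 45.7 = 91.4 (stated 91.3). Linear scaling is adequate.

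**600 mg BID against both limits.**

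| Ka, F | Upper Cmax (limit 22.1) | Upper AUC (limit 250) | Mean Cmax | Mean Cmax / 6.05 | Mean AUC (cap 145) |
|---|---|---|---|---|---|
| 1.3, 1 | 16.1, passes | 145, passes | 11.0 | 1.82, breaks | 91.3 |
| 0.6, 1 | 11.5, passes | 145, passes | 8.19 | 1.35, breaks | 91.3 |
| 1.3, 0.5 | 8.05, passes | 72.5, passes | 5.49 | 0.91, complies | 45.7 |

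The other six rows of Table 5 meet both limits. No row exceeds a mean AUC of 145, so within the table the conflict is in Cmax only. At 600 mg BID the cap is broken when F exceeds 6.05/11.0 = 0.55 (Ka 1.3) or 6.05/8.19 = 0.74 (Ka 0.6).

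**What Part A implies.** The protocol gives no Part A estimates of F and Ka, but the synopsis reports single doses of 200, 600 and 1200 mg.

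- *Ka 1.3, F 1.* Section 4.5 predicts Cmax 3.4 (upper 5.0) at 200 mg. Six times this is 20.4 (upper 30.0) at 1200 mg, above 22.1. If the Part A rule was met, the 1.82 case is unlikely.
- *Ka 0.6, F 1.* No single-dose prediction is given, so the 300 mg OD steady-state row serves as a proxy: 4 × 3.83 = 15.3, upper 4 × 5.42 = 21.7, upper AUC 4 × 36.2 = 144.8. All are within the rule, so the 1.35 case stays open.
- *Median aim of about 6 met at 600 mg.* The predicted Cmax at Ka 1.3, F 1 is 3 × 3.4 = 10.2. The scaling 6/10.2 = 0.588 gives 0.588 × 11.0 = 6.47 at 600 mg BID, or 1.07 times the cap.
- *Median aim met at 1200 mg.* The scaling 6/20.4 = 0.294 gives 0.294 × 11.0 = 3.24, or 0.53 times, which complies.

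**Outer bound.** The largest BID dose the rule permits is the smaller of 600 × 22.1/upper Cmax and 600 × 250/upper AUC. In the table's row order this is 824, 1034 and 1647 mg. The doses that would meet the Cmax cap are 600 × 6.05/mean Cmax = 330, 443 and 661 mg, so the ratios are 2.50, 2.33 and 2.49. Mean AUC at the rule's ceiling is about 125, 157 and 125; only the second exceeds 145 (1.09 times). These ceilings amount to 1.65 to 3.29 g/day, and Section 4.6 regards even 1.2 g/day as unlikely to be exceeded. They bound what the rule allows and do not predict what will be given.

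**The case against.** The strongest reply is that two maxima can coexist. The 22.1/250 limits are ceilings and do not license dosing up to them, and Section 4.6.1 is also current text, so the stricter limit applies and only a cross-reference is missing. As a reading of the whole protocol this is fair. It fails in practice because the committee's section states 22.1/250 and nothing there or in Section 9.3.2.1 points to 6.05/145.

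Several other points stand and limit the size of the problem:

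- Table 5 gives example doses under assumptions chosen before Part A. Section 4.5 says Ka 1.3 and F 100% were taken to give the highest possible exposure. The amendment log shows the testicular row was added later, alongside the Part A results, so 6.05/145 may be a forecast informed by those data. The document does not settle this.
- The cases within 0.53 to 1.35 are not equally likely. The 1.35 case implies a Part A Cmax of about 7.7 at 600 mg (2 × 3.83) and 15.3 at 1200 mg, both above the aim of about 6. The 1.07 case implies about 12 at 1200 mg.
- The same row reports reassuring data: no testicular change in a second similar rat study, in a longer rat study of the active compound, in dogs with either compound, or in the 28-day rat study of GSK3039294 up to 1000 mg/kg/day, the dose level tied to 22.1/250.
- The numerical sentence in Section 9.3.2.1 covers Part A only. The rules governing the remaining doses are those in Sections 4.5, 6.3 and 10.7.1.

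The animal data support re-basing the conclusion. They do not justify keeping a written limit that the dosing rules fail to enforce.

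**Conclusion.** The concern holds and should be fixed before the remaining Part B and Part C doses are chosen. The mismatch is certain from the text, and the protocol's own 600 mg BID example at F = 1 passes the dosing rule while exceeding the promised mean Cmax by a factor of 1.82 or 1.35.

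Whether a real dose would breach is not known. At 1.2 g/day the plausible range is about 0.53 to 1.35 times the cap, so a small breach or none is possible. That range assumes linear kinetics, Table 5's profile shapes, a median close to the mean, and that Part A followed its own rule. Harm is not shown. The defect is that the limit supporting a written safety conclusion is not the limit used to set doses.

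**What to change.** Preferred: add predicted mean Cmax ≤ 6.05 µg/mL and AUC0-24 ≤ 145 µg·h/mL as binding limits, alongside 22.1/250, in Section 4.5 (Parts B and C), Section 6.3 and Section 10.7.1. Repeat them in the part of Section 9.3.2.1 that covers later study parts. Then re-check 600 mg BID with the Part A estimates of F and Ka.

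Alternative, if 22.1/250 is meant to govern: remove the 6.05/145 commitment from Section 4.6.1 and rest the risk conclusion explicitly on the oral 28-day rat data for GSK3039294 at the NOAEL linked to 22.1/250. Because this drops the stricter commitment, the toxicology source should be reviewed first.

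Either route costs protocol wording; the preferred one also needs a re-run of existing simulations. Neither needs extra subjects or procedures. The preferred route may lower the top dose: under Table 5's assumptions the cap would fall at about 330 mg BID (Ka 1.3, F 1), 443 mg BID (Ka 0.6, F 1) or 661 mg BID (Ka 1.3, F 0.5).
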